5.2 General Concomitant Medication and Supportive Care Guidelines

Patients should receive full supportive care during the study, including transfusion of blood and blood products, and treatment with antibiotics, analgesics, erythropoietin, or bisphosphonates, when appropriate.

Anti-emetics (such as prochlorperazine, lorazepam, ondansetron or other 5-HT₃ antagonists) may be administered prophylactically in the event of nausea. Anti-diarrheals, such as loperamide, may be administered as needed in the event of diarrhea. Although acetaminophen at doses of ≤ 2 g/day is permitted, it should be used with caution in subjects with impaired liver function.

5.2.1 Anticoagulants

Results from drug-drug interaction studies conducted in subjects with cancer suggest that pazopanib has no effect on the metabolism of S-warfarin. Hemorrhagic events, however, have been reported in clinical studies with pazopanib; therefore, pazopanib should be used with caution in subjects with increased risk of severe bleeding or who are receiving concomitant anticoagulant therapy (e.g., warfarin or its derivatives, low molecular weight heparin, unfractionated heparin). Subjects taking concomitant anticoagulant therapy should be monitored regularly for changes in relevant coagulation parameters as clinically indicated, as well as for any clinical bleeding episodes.

5.2.2 Hypoglycemic Therapy

Results from drug-drug interaction studies conducted in subjects with cancer suggest that there will be no clinically relevant pharmacokinetic interaction between pazopanib and hypoglycemic agents. Transient decreases in serum glucose (mainly Grade 1 and 2, rarely Grade 3) have been observed in clinical studies with pazopanib. In addition, decreases in blood sugar have been recently reported in subjects treated with another small molecule tyrosine kinase inhibitor, sunitinib[31]. Such changes may require an adjustment in the dose of hypoglycemic and/or insulin therapy. Subjects should be advised to report symptoms of hypoglycemia (e.g., confusion, visual disturbances, palpitations, sweating). Serum glucose should be tested during treatment with pazopanib as outlined in the protocol and as clinically indicated.

5.2.3 Use of Statins

Concomitant use of pazopanib and simvastatin increases the risk of ALT elevations. If a patient receiving concomitant simvastatin develops ALT elevations, follow guidelines for pazopanib dose modification and discontinue simvastatin. Insufficient data are available to assess the risk of concomitant administration of alternative statins and pazopanib.

5.2.4 Medications that Raise Gastric pH

In a drug interaction trial in patients with solid tumors, concomitant administration of pazopanib with esomeprazole, a proton pump inhibitor, decreased the exposure of pazopanib by approximately 40% (AUC and C_{max}). Therefore, concomitant use of pazopanib with drugs that raise gastric pH should be avoided. If such drugs are needed, short-acting antacids such as Tums, Rolaids, Maalox, and Mylanta should be considered in place of proton pump inhibitors and H₂ receptor antagonists. Separate antacid and pazopanib dosing by several hours to avoid a reduction in pazopanib exposure.

5.2.5 Medications to Use with Caution

In vitro data indicate that pazopanib is a potential inhibitor for CYP3A4, CP2C8,

CYP2D6, CYP1A2, CYP2C9, CYP2C19, CYP2A6, CYP2B6, and CYP2E1. Pregnane X receptor transient transfection assay suggested some potential for human CYP3A4 induction at high concentrations. Results from drug-drug interaction studies conducted in subjects with cancer suggest that pazopanib is a weak inhibitor of CYP3A4, CYP2C8, and CYP2D6 *in vivo*, but had no clinically relevant effect on CYP1A2, CYP2C9, or CYP2C19 metabolism. Therefore, concomitant use of pazopanib with certain medications (substrates of CYP3A4, CYP2C8, and CYP2D6) with a narrow therapeutic window should be undertaken with **CAUTION** due to the potential for alterations in the pharmacologic effects of these medications or an increased risk for serious or life threatening adverse events associated with such medications (see below) secondary to the inhibition of specific CYP enzymes by pazopanib. In addition, the potential for drug interaction with such medications, although diminished, may persist after the last dose of pazopanib due to its long half-life (i.e., mean 30.9 hours); therefore, continue to exercise **CAUTION** for at least 7 days and up to 15 days after the last dose of pazopanib when administering these medications. These medications include (but are not limited to):

- Ergot derivatives: dihydroergotamine, ergonovine, ergotamine, methylergonovine (potential increased risk for developing ergot toxicity that includes severe vasospasm leading to peripheral as well as cerebral ischemia)
- Neuroleptics: pimozide (potential increased risk for QT interval prolongation, ventricular arrhythmia, and sudden death)
- Antiarrhythmics: bepridil, flecainide, lidocaine, mexiletine, amiodarone, quinidine, propafenone (potential increased risk for QT interval prolongation and Torsade de Pointes)
- Immune modulators: cyclosporine, tacrolimus, sirolimus (potential increased risk for nephrotoxicity and neurotoxicity)
- Miscellaneous: quetiapine, risperidone, clozapine, atomoxetine.

The results from *in vitro* studies suggested that the oxidative metabolism of pazopanib in human liver microsomes is mediated primarily by CYP3A4, with minor contributions from CYP1A2 and CYP2C8. Furthermore, *in vitro* data suggest that pazopanib is a substrate for p-glycoprotein. Substances that induce or inhibit CYP3A4 may alter the pharmacologic effects of pazopanib and should be used with **CAUTION**.

Medications that inhibit CYP3A4 may result in increased plasma pazopanib concentrations. Co-administration of strong CYP3A4 inhibitors is prohibited (see Section 5.2.5); therefore selection of an alternate concomitant medication with no or minimal potential to inhibit CYP3A4 is recommended.

CYP3A4 inducers may decrease plasma pazopanib concentrations. Selection of an alternate concomitant medication with no or minimal enzyme induction potential is recommended.

Drugs that induce CYP3A4 and may decrease pazopanib plasma concentrations include (but are not limited to):

- Glucocorticoids: cortisone (>50 mg), hydrocortisone (>40 mg), prednisone (>10 mg), methylprednisolone (>8 mg), dexamethasone (>1.5 mg)
- Anticonvulsants: phenytoin, carbamazepine, phenobarbital, oxcarbazepine
- HIV antivirals: efavirenz, nevirapine
- Antibiotics: rifampin (rifampicin), rifabutin, rifapentene
- Miscellaneous: St. John's Wort, modafinil, pioglitazone

5.2.6 Prohibited Medications

Medications that inhibit CYP3A4 may result in increased plasma pazopanib concentrations; therefore, co-administration of strong CYP3A4 inhibitors is **PROHIBITED** beginning 14 days prior to the first dose of study drug until discontinuation from the study. **Strong CYP3A4 inhibitors include (but are not limited to):**

- Antibiotics: clarithromycin, telithromycin, troleandomycin
- HIV: protease inhibitors (ritonavir, indinavir, saquinavir, nelfinavir, lopinavir)
- Antifungals: itraconazole, ketoconazole, voriconazole
- Antidepressants: nefazodone

Refer to <http://medicine.iupui.edu/clinpharm/ddis/main-table/>

In vitro studies suggested that pazopanib is a substrate of P-glycoprotein (P-gp) and breast cancer resistance protein (BCRP). Therefore, absorption and subsequent elimination of pazopanib may be influenced by products that affect P-gp and BCRP.

Concomitant treatment with strong inhibitors of P-gp or BCRP should be avoided due to risk of increased exposure to pazopanib. Selection of alternative concomitant medicinal products with no or minimal potential to inhibit P-gp or BCRP should be considered.

5.3 Women of Childbearing Potential

Women of childbearing potential (defined as women with regular menses, women with amenorrhea, women with irregular cycles, women using a contraceptive method that precludes withdrawal bleeding, and women who have had a tubal ligation) are required to have a negative serum pregnancy test within 14 days prior to the first dose of pazopanib.

Female patients are required to use two forms of acceptable contraception, including one barrier method, during participation in the study and for 28 days following the last dose of pazopanib.

If a patient is suspected to be pregnant, pazopanib should be immediately discontinued. In addition a positive urine test must be confirmed by a serum pregnancy test. If it is confirmed that the patient is not pregnant, the patient may resume dosing.

If a female patient becomes pregnant during therapy or within 28 days after the last dose of pazopanib, the investigator must be notified in order to facilitate outcome follow-up.

5.4 Duration of Therapy

If at any time the constraints of this protocol are considered to be detrimental to the patient's health and/or the patient no longer wishes to continue protocol therapy, the protocol therapy should be discontinued and the reason(s) for discontinuation documented in the case report forms.

In the absence of treatment delays due to adverse events, treatment may continue indefinitely until one of the following criteria applies:

- Documented and confirmed disease progression
- Death
- Adverse event(s) that, in the judgment of the investigator, may cause severe or permanent harm or which rule out continuation of study drug
- General or specific changes in the patient's condition render the patient unacceptable for further treatment in the judgment of the investigator
- Suspected pregnancy
- Serious non-compliance with the study protocol
- Lost to follow-up
- Patient withdraws consent
- Investigator removes the patient from study
- The Siteman Cancer Center decides to close the study

Patients who prematurely discontinue treatment for any reason other than withdrawal of consent will be followed as indicated in the study calendar.

5.5 Duration of Follow-up

After cessation of study treatment, patients will be followed every 3 months until death. Either phone contact or review of the Social Security Death Index is acceptable to monitor for overall survival. Patients removed from study for unacceptable adverse events will be followed until resolution or stabilization of the adverse event.

6.0 DOSE DELAYS/DOSE MODIFICATIONS

As a general rule, if dose reduction of pazopanib is necessary, the dose should be reduced stepwise by 200 mg at each step, and the patient should be monitored for approximately 10 to 14 days at each dose level. If toxicity does not abate during this monitoring time, the pazopanib may need to be interrupted and/or the dose further decreased with continued monitoring for an additional 10-14 days at each dose level, and so on.

If the toxicity has abated with reduction of the dose and dose re-escalation is considered safe by the investigator, the pazopanib dose can then be increased step-wise back to the pre-event dose (in 200 mg increments, after monitoring for 10-14 days at each dose level to ensure that toxicity did not recur or worsen).

Dose Modification Algorithms for Potential Treatment-Related Adverse Events

AE Terms & Descriptions	Dose Modification Algorithms
Hypertension	
(A). Asymptomatic and persistent SBP of ≥ 140 - < 170 mmHg, or DBP ≥ 90 - < 110 mmHg, or a clinically significant increase in DBP of 20 mmHg (but still below 110 mmHg).	Step 1. Continue pazopanib at the current dose. Step 2. Adjust current or initiate new antihypertensive medication(s). Step 3. Titrate antihypertensive medication(s) during next 2 weeks as indicated to achieve well-controlled ^a blood pressure (BP). If BP is not well-controlled within 2 weeks, consider referral to a specialist and go to scenario (B).
(B). Asymptomatic SBP ≥ 170 mmHg, or DBP ≥ 110 mmHg, or failure to achieve well-controlled BP within 2 weeks in scenario (A). (A).	Step 1. Consider reducing or interrupting pazopanib, as clinically indicated. Step 2. Adjust current or initiate new antihypertensive medication. Step 3. Titrate antihypertensive medication(s) during next 2 weeks as indicated to achieve well-controlled BP. Step 4. Once BP is well-controlled, restart pazopanib dose-reduced by 200 mg if it was interrupted.
(C). Symptomatic hypertension or recurring SBP ≥ 170 mmHg, or DBP ≥ 110 mmHg, despite modification of antihypertensive medication(s)	Step 1. Interrupt pazopanib. Step 2. Adjust current or initiate new antihypertensive medication(s). Step 3. Titrate antihypertensive medication(s) during next 2 weeks as indicated to achieve well-controlled BP. Referral to a specialist for further evaluation and follow-up is also recommended. Step 4. Once BP is well-controlled, restart pazopanib dose-reduced by 200 mg.
(D). Refractory hypertension unresponsive to above interventions.	Discontinue pazopanib and continue follow-up per protocol.
Proteinuria	
UPC < 3	Continue pazopanib at the current dose; monitor as clinically indicated
UPC ≥ 3 or 24-h urine protein ≥ 3 g	Step 1. Interrupt pazopanib. Step 2. Weekly UPC or 24-hr urine protein monitoring until

AE Terms & Descriptions	Dose Modification Algorithms
	
UPC is <3 or 24-hr urine protein is <3 g. Then restart pazopanib dose-reduced by 200 mg.
 
Step 3. If UPC ≥ 3 or 24-h urine protein ≥ 3g recurs, repeat steps 1 and 2
 
Step 4. If UPC ≥ 3 or 24-hr urine protein ≥ 3 recurs and the pazopanib dose can no longer be reduced, discontinue pazopanib and continue follow-up per protocol.

Hemorrhage/Bleeding: Investigate and document underlying etiology of the bleeding	
Grade 1	
For hemoptysis, interrupt pazopanib and consider whether further treatment with pazopanib is appropriate.
 
For other grade 1 hemorrhage/bleeding event, continue pazopanib at the current dose; monitor as clinically indicated.

Grade 2	
Step 1. If pulmonary or GI bleed (other than hemorrhoidal bleeding), discontinue pazopanib and continue follow-up per protocol. Otherwise, interrupt pazopanib until the AE resolved to \leq grade 1.
 
Step 2. Restart pazopanib; consider reducing dose and monitor as clinically indicated.

Grade 3 or 4, or recurrent \geq grade 2 event after dose interruption/reduction.	Discontinue pazopanib and continue with follow-up per protocol.
Venous Thrombosis (DVT, PE)	
Grade 2	Continue pazopanib at the current dose; monitor as clinically indicated
Grade 3	
Step 1. Interrupt pazopanib.
 
Step 2. Initiate and monitor anticoagulation as clinically indicated.
 
Step 3. Resume pazopanib at reduced dose only if all of the following criteria are met:
 
 • The subject must have been treated with anticoagulant at the desired level of anticoagulation for at least one week. • No grade 3 or 4 or clinically significant grade 2 hemorrhagic events have occurred while on anticoagulation treatment. 
Subject should be monitored as clinically indicated during anticoagulation treatment and after resuming study treatment. When treating with warfarin, international normalized ratio (INR) should be monitored within three to five days after any change in pazopanib dosing (e.g., re initiating, escalating/de-escalating, or discontinuing pazopanib), and then at least weekly until the INR is stable. The dose of warfarin (or its derivatives) may need to be adjusted to maintain the desired level of anticoagulation

Grade 4 and/or PE	Discontinue pazopanib and continue follow-up per protocol.
Arterial Thrombosis/Ischemia	

AE Terms & Descriptions	Dose Modification Algorithms
Any grade	Discontinue pazopanib and continue follow-up per protocol.
Thrombocytopenia: Investigate and document underlying cause	
Grade 1 or 2	Continue pazopanib with current dose; monitor as clinically indicated.
Grade 3 or 4	Step 1. Interrupt pazopanib until toxicity resolves to \leq grade 2. Step 2. Restart pazopanib dose-reduced by 200 mg and monitor as clinically indicated. If no recovery to \leq grade 2 or recurrent grade 3 or 4 thrombocytopenia, discontinue pazopanib and follow-up per protocol
Anemia: No specific dose reduction rules are indicated for anemia unless due to hemorrhage or bleeding as noted above.	

Palmar-plantar Erythrodysesthesia Syndrome	
Grade 1 Minimal skin changes or dermatitis without pain (erythema, edema, hyperkeratosis)	Continue pazopanib with current dose.
Grade 2 Skin changes with pain; limiting instrumental activities of daily living (peeling, blisters, edema, bleed, hyperkeratosis)	Step 1. Hold pazopanib. Step 2. Treat as clinically appropriate. Step 3. Upon resolution to grade 1 or better, restart pazopanib with a dose reduction to 400 mg. Step 4. If recurrent, consider a further dose reduction to 200 mg or discontinuation.
Grade 3 Severe skin changes with pain and limiting self-care activities of daily living	Discontinue pazopanib
Other Clinically Significant Drug-Related Adverse Events^b	
Grade 1	Continue pazopanib; monitor as clinically indicated.
Grade 2 or 3, if clinically significant	Step 1. Interrupt pazopanib until toxicity resolves to \leq Grade 1. Step 2. Restart pazopanib dose-reduced by 200 mg and monitor as clinically indicated.
Grade 4	Discontinue pazopanib and continue follow-up per protocol. (study drug can be interrupted for up to 28 days)
Prolongation of QTc Interval: If the QTc is prolonged, the ECG should be manually read to ensure accuracy of the reading. The values below refer to manually-read ECGs.	
QTc \geq 480-500 msec	Continue pazopanib; monitor as clinically indicated.
QTc \geq 500 msec	Discontinue pazopanib and continue follow-up per protocol.

a. Well-controlled BP defined as SBP <140 mmHg and mean DBP <90 mmHg.

b. AEs are graded according to NCI Common Terminology Criteria for Adverse Events v4.0 (NCI CTCAE v4)

Guidelines for Management of Treatment Emergent Hepatotoxicity

Event	Dose Modification Algorithms
(A). ALT of $\leq 3.0 \times \text{ULN}$	Continue pazopanib at current dose with full panel LFTs ^a monitored as per protocol.
(B). ALT $>3.0 \times \text{ULN}$ to $\leq 8.0 \times \text{ULN}$ without bilirubin elevation (defined as total bilirubin ^b $<2.0 \times \text{ULN}$ or direct bilirubin $\leq 35\%$) and without hypersensitivity symptoms (e.g., fever, rash)	Step 1. Continue pazopanib at current dose levels. Step 2. Monitor subject closely for clinical signs and symptoms; perform full panel LFTs ^a weekly or more frequently if clinically indicated until ALT is reduced to grade 1.
(C). ALT $>8.0 \times \text{ULN}$ without bilirubin elevation (defined as total bilirubin ^b $<2.0 \times \text{ULN}$ or direct bilirubin $\leq 35\%$) and without hypersensitivity symptoms (e.g., fever, rash)	
1st occurrence – Liver Event Interruption Criteria:
 
Step 1. Interrupt pazopanib until toxicity resolves to \leq grade 1 or baseline. Report the event to Novartis as an SAE within 24 hours of learning of its occurrence. Make every reasonable attempt to have subjects return to the clinic within 24 to 72 hours for repeat liver chemistries and liver event follow up assessments.
 
Step 2. Liver imaging and other laboratory investigations should be considered as clinically appropriate.
 
Step 3. Monitor subject closely for clinical signs and symptoms; perform full panel LFTs^a weekly or more frequently if clinically indicated until ALT is reduced to grade 1.
 
Step 4. If the subject is benefiting from the study treatment, re-treatment with pazopanib at 400 mg may be considered if ALL following criteria are met:
 
 - ALT reduced to Grade 1 - Total bilirubin $<1.5 \times \text{ULN}$ or direct bilirubin $\leq 35\%$ - No hypersensitivity signs or symptoms - Subject is benefiting from therapy. 
Recurrence – Liver Event Stopping Criteria:
 
Discontinue pazopanib permanently and monitor subject closely for clinical signs and symptoms; perform full panel LFTs^a weekly or more frequently if clinically indicated until ALT is reduced to grade 1.

Event	Dose Modification Algorithms

(D). ALT >3.0 x ULN with concomitant elevation in bilirubin^b (defined as total bilirubin ≥2.0 x ULN; with direct bilirubin >35%) or with hypersensitivity symptoms (e.g., fever, rash).
	
Liver Event Stopping Criteria:
 
Step 1. Discontinue pazopanib immediately; report the event to Novartis as an SAE within 24 hours of learning of its occurrence. Make every reasonable attempt to have subjects return to the clinic within 24 hours for repeat liver chemistries and liver event follow up assessments.
 
Step 2. Consult a gastroenterologist / hepatologist and perform the following assessments to identify potential co-factors:
 
 - Eosinophil count - Viral serology for hepatitis A, B, C and E, cytomegalovirus, Epstein-Barr virus (IgM antibody, heterophile antibody, or monospot testing) - Anti-nuclear antibody, anti-smooth muscle antibody, Type 1 anti-liver kidney microsomal antibodies. - Serum creatinine phosphokinase for possible muscle injury caused LFT elevation - Liver imaging - Consider toxicological blood screen for possible contributing chemical/medical entities 
Step 3. Monitor subject closely for clinical signs and symptoms; record the appearance or worsening of clinical symptoms of hepatitis, or hypersensitivity, such as fatigue, nausea, vomiting, right upper quadrant pain or tenderness, fever rash or eosinophilia as relevant on the AE report form. Perform full panel LFTs^a weekly or more frequently if clinically indicated until LFTs are reduced to grade 1.

For isolated total bilirubin^b elevation without concurrent ALT increases (defined as ALT < 3 X ULN).
	
Step 1. Isolated hyperbilirubinemia (i.e., in the absence of elevated ALT or other signs/symptoms of liver injury) does not require dose modification. Pazopanib inhibits UGT1A1 and OATP1B1, which can cause elevation of indirect (unconjugated) bilirubin in the absence of liver injury.
 
Step 2. If bilirubin is >1.5 x ULN in the absence of ALT elevation, fractionation of bilirubin elevation should be performed. If bilirubin is >35% direct (conjugated), further evaluation for underlying cause of cholestasis should be performed.

- a. Full panel LFTs include: AST, ALT, alkaline phosphatase, and total bilirubin. Coagulation tests should be performed as clinically indicated.
- b. Serum bilirubin fractionation should be performed if testing is available. If testing is unavailable and a subject meets the criterion of total bilirubin >1.5 x ULN, then the event should be promptly reported as an SAE.

Please see Section 7.8 for adverse event reporting instructions for hepatotoxicity.

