10.0 STUDY CALENDAR

Screening assessments must be performed no more than 14 days prior to start of study treatment, except scans which may take place up to 28 days prior to the start of treatment. After the start of study treatment, there is a ± 7 day window for all exams, scans, labs and procedures to be performed. Please note, there is also a ± 7 day window for treatment and for routine office visits.

	Screening	D1 of each cycle	C1D5	C1D8	C1D9	C1D15 and C2D15	End of every even-numbered cycle	EOT	F/U ¹	
Informed consent	X									
PE, H&P, PS	X	X						X		
VS	X	X		X				X		
CBC	X	X		X				X		
CMP	X	X		X				X		
LFTs ²	X	X ²		X ²		X ²		X		
Pregnancy test ³	X							X		
UPC	X	X ⁴						X		
TSH, FT4	X	X ⁵								
PT/PTT, INR	X							X		
ECG	X	X ⁶								
ECHO ¹⁰	X									
CT scan	X						X	X		
Pazopanib		X	-----					X ⁷		
FACT-G		X ⁸				X ⁸				
Blood for biomarkers		X ⁹								
Collect/review drug diary		X								
Toxicity assessment	X	X						X		

1. Every 3 months until death.

2. Monitor serum liver tests (total bilirubin, ALT/AST) before initiation of treatment with pazopanib and on C1D15, C2D1, C2D15, C3D1, C4D1, C5D1, and as clinically indicated (± 3 days). Periodic monitoring should continue after C5.

3. Women of childbearing potential only.

4. D1 of each cycle through C6, then D1 of every even-numbered cycle thereafter.

5. Monitor between every 8 to every 16 weeks.

6. C2D1, C4D1, C7D1, and then every 16 weeks (D1 of every 4th cycle) until EOT.

7. To be taken PO each day. Each cycle is 4 weeks long. See Section 5.1 for dosing instructions.

8. Baseline (prior to C1D1), C1D15, and D1 of every cycle thereafter.

9. Baseline (prior to C1D1), C2D1, C3D1, and C4D1.

10. Baseline (prior to C1D1) and periodic reassessment as needed and/or as indicated. Consistent diagnostic imaging should be used throughout study.

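### Cheap patient-safety improvement, not an error: add scheduled blood pressure at C1D15 and C2D15, because the calendar leaves nominal gaps of 21 and 28 days early in treatment at 800 mg

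*Combined protocol and SAP*

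**What the plan says.** Section 6.0 (Hypertension) has two tiers for BP without symptoms. Scenario (A) covers "Asymptomatic and persistent SBP of ≥ 140 - < 170 mmHg, or DBP ≥ 90 - < 110 mmHg": pazopanib continues and antihypertensives are started or adjusted. Scenario (B) covers "Asymptomatic SBP ≥ 170 mmHg, or DBP ≥ 110 mmHg", or failure to control BP under (A): the investigator considers reducing or interrupting pazopanib. Step 3 of scenario (A) reads "Titrate antihypertensive medication(s) during next 2 weeks as indicated to achieve well-controlled" BP.

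The vital-signs (VS) row of the Section 10.0 calendar is marked at screening, Day 1 of each cycle, C1D8 and end of treatment. The column for C1D15 and C2D15 exists, but VS is blank there. That column carries liver tests, and FACT-G at C1D15 only (footnote 8).

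Footnote 2 on liver tests says "Monitor serum liver tests (total bilirubin, ALT/AST) before initiation of treatment with pazopanib and on C1D15, C2D1, C2D15, C3D1" and later days, with its own window: "on C1D15, C2D1, C2D15, C3D1, C4D1, C5D1, and as clinically indicated (± 3 days". For everything else "there is a ± 7 day window for all exams, scans, labs and procedures to be performed", and "there is also a ± 7 day window for treatment and for routine office visits".

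Section 5.1 and the Cycle 1 diary give 200 mg BID on Days 1–4, 400 mg BID on Days 5–8 and 800 mg QD from Day 9. No other section schedules an on-treatment BP. The drug diaries have no BP field, and no home monitoring is described.

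**The concern.** A threshold defined by the absence of symptoms can be acted on only if someone takes a reading. With the calendar followed exactly, the first scheduled BP on 800 mg QD is at C2D1, nominally Day 29, and the next is at C3D1, Day 57. New hypertension without symptoms, including the upper tier where a dose decision is to be considered, could go unseen for three to four weeks. C1D8 is an early check, but it is nominally only the fourth day at a total of 800 mg/day.

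The stake is patient safety. Section 1.3 describes the target population as elderly and debilitated, and Section 3.1 admits ECOG 2 and patients on anticoagulants. In the same eight weeks liver tests are listed every 14 days, so the calendar already has suitable dates at which to take a BP.

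**Working it through.** **Inputs.** Cycle length 28 days (Section 5.1); VS marks, liver-test days and windows (Section 10.0). 'VS' is not defined in the documents; I take it to include BP. The plan states no figure of its own here to reproduce.

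**Study days.** Day = (cycle − 1) × 28 + day of cycle. C1D8 = 8, C1D15 = 15, C2D1 = 29, C2D15 = 43, C3D1 = 57.

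**Nominal gaps now.** Readings on Days 1, 8, 29 and 57: gaps of 8 − 1 = 7, 29 − 8 = 21 and 57 − 29 = 28 days. Days without a scheduled BP: 9–28 (20 days, the first 20 on 800 mg QD) and 30–56 (27 days).

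**Nominal gaps with BP at C1D15 and C2D15.** Readings on Days 1, 8, 15, 29, 43 and 57: gaps of 7, 7, 14, 14 and 14 days. The longest gap falls from 28 to 14 days, and the longest run of days without a scheduled BP from 27 to 13 (Days 16–28, and likewise 30–42 and 44–56).

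**With visit windows.** The range of a gap is the nominal gap ± the sum of the windows at its two ends. The text allows three readings. The added BPs carry ±3 days in each.

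| Reading of the windows | C1D8–C2D1 now | C2D1–C3D1 now | 14-day gaps after the change | Worst case, now to after |
|---|---|---|---|---|
| ±7 at C1D8 and Day 1, calendar fixed to C1D1 | 21 ± (7+7) = 7–35 | 28 ± (7+7) = 14–42 | 14 ± (3+7) = 4–24 | 42 to 24 |
| ±7, each cycle counted from its actual Day 1 | 7–35 | 28 ± 7 = 21–35 | C2D1–C2D15: 14 ± 3 = 11–17; the other two: 4–24 | 35 to 24 |
| Day 1 BP taken with the ±3-day liver draw, fixed calendar | 21 ± (7+3) = 11–31 | 28 ± (3+3) = 22–34 | 14 ± (3+3) = 8–20 | 34 to 20 |

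C1D8–C1D15 becomes 7 ± (7+3), that is 0–17 days, since a gap cannot be negative. In the third row C1D8 keeps ±7 because the list in footnote 2 does not name it.

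**Does the ±3 matter?** If the added readings took the general ±7, the 14-day gaps on a fixed calendar would be 14 ± (7+7) = 0–28 days. The narrower window is therefore part of the change.

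**Burden.** 2 readings × 56 patients (Section 15.1) = 112 at most. The real number is smaller: Section 9.3 says that pharmacokinetic testing, limited to the first 11 patients at the coordinating site, is already complete.

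**The case against.** The strongest reply is that nothing here is wrong. CBC and CMP follow the same Day 1 plus C1D8 pattern as VS, and urine protein (UPC) is on "D1 of each cycle through C6, then D1 of every even-numbered cycle thereafter", so the schedule is coherent. Liver-test timing is set for a different toxicity and is no benchmark for BP. The documents give no onset time or incidence for hypertension, so they cannot show that 14 days is needed before C3D1 while 28 days is acceptable afterwards. All of this stands. It is why the point is an improvement and not a defect, and why the choice of dates rests on convenience.

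A reader might infer that the calendar contradicts Section 6.0, because a two-week titration cannot be run on four-weekly readings. The documents do not support that. Titrating to a target implies unscheduled readings once raised BP is found, and nothing in the calendar forbids them. The gap is in scheduled detection only, and Step 3 of scenario (A) needs no change.

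A reader might also take 42 to 24 days as the settled worst case. It is one of three readings of the windows; taking Day 1 BP with the liver draw gives 34 to 20.

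Existing safeguards count for something: exclusion criterion 13 sets BP limits at entry, the toxicity form is continuous (Section 11.0), and serious toxicities are monitored on an ongoing basis (Section 13.0). None of them supplies a scheduled reading between C1D8 and C2D1 or between C2D1 and C3D1.

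Finally, one reading cannot establish the persistence that scenario (A) requires. That is correct, and the change below includes a repeat.

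**Conclusion.** The point holds as a low-cost patient-safety improvement. To Week 8 the plan schedules four on-treatment BPs, with nominal gaps of 21 and 28 days, although it acts on BP without symptoms from 140/90 and again from 170/110. Two added readings halve the longest nominal gap to C3D1, from 28 to 14 days, and shorten the worst case under every reading of the windows.

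This assumes that VS includes BP and that sites take no unscheduled readings before raised BP is found. Sites that already measure BP at the mid-cycle draws would gain nothing.

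Three further inferences are not supported. The number of patients with missed or late-treated hypertension cannot be estimated, since the documents give neither incidence nor onset. No effect on the 16-week clinical benefit rate is shown or claimed. The change does not cover later cycles: spacing from C3D1 onward stays at 28 days.

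**What to change.** In the VS row of the Section 10.0 calendar, mark the C1D15 and C2D15 column with this footnote: *BP only, taken with the LFT draw (± 3 days); repeat if elevated to confirm persistence.* Scenarios (A) to (D), the toxicity assessments and the schedule from Cycle 3 can stay as they are.

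Cost: at most two extra cuff readings for each patient still to be treated, plus any repeats. The documents do not say whether C1D15 and C2D15 are clinic visits or lab-only draws; if lab-only, someone must be available to take the reading. The edit is one calendar mark and one footnote, but under Section 16.0 it is a protocol modification that goes to the secondary sites and their IRBs, so it is sensibly bundled with the next amendment.
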